## **2.4 Determination of sample size**

Subjects will be randomized in a 1:1 ratio to the CZP 200mg Q2W and placebo treatment groups. The expected response rates for ASDAS-MI at Week 52 are 40% and 20% for CZP and placebo, respectively. A total sample size of 300 (150 subjects per treatment group) provides 95% power to detect a statistically significant difference in the ASDAS-MI response rate at Week 52 between CZP and placebo based on a 2-sided significance level of 0.05.

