#### **3.5.3 Safety Set**

The Safety Set (SS) will consist of all subjects in the RS who have received at least one dose of study medication.

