### 3.6 Treatment assignment and treatment groups

At Baseline, eligible subjects will be randomly assigned in a 1:1 ratio to the following double-blind study treatments:

- Placebo (PBO)
- CZP administered sc at the loading dose of CZP 400mg Q2W at Weeks 0, 2 and 4 followed by CZP 200mg Q2W (starting at Week 6)

For presentation purposes, the terms CZP 200mg Q2W and PBO will be used.

For disposition, demography, Baseline characteristics and protocol deviations, in addition to the CZP 200mg Q2W and PBO groups, an all subjects group (CZP 200mg and PBO combined) will be displayed.

In general, for by visit data collected during the open-label period, subjects will be presented according to the treatments received in the double-blind period (CZP 200mg Q2W and PBO). For the by visit data collected during the SFE period, subjects will be presented in a single CZP 200mg Q2W treatment group.

Concomitant medications will be summarized according to whether they were taken: during the double-blind period by CZP 200mg Q2W or PBO, or during the open-label period by PBO->OL CZP (subjects who were randomized to PBO and then received open-label CZP), CZP->OL CZP (subjects who were randomized to CZP and then received open-label CZP)- or by the OL-OT group. In addition, concomitant medications taken during any CZP medication period of the main study (Total CZP incl DB and OL) and all concomitant medications (All subjects, including OL-OT but excluding SFE) will also be summarized. See [Section 6.4](#) for more detail.

AEs will be assigned to periods based on whether they started during the double-blind, OL-CZP, OL-OT, or SFE periods. Data corresponding to the OL-OT group will not be summarized, but only presented in listings. AEs will be summarized as follows:

- Double-blind period by CZP 200mg Q2W or PBO,
- Open-label CZP period by PBO->OL CZP or CZP->OL CZP (as above),
- SFE period by OL CZP
- Total CZP incl DB and OL (includes randomized CZP 200mg Q2W and AEs starting in the open-label CZP period).
- Total CZP incl DB, OL, and SFE OL (includes randomized CZP 200mg Q2W, AEs starting in the open-label CZP period and AEs starting in the SFE period).

See [Section 11.2](#) for more detail.

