If it is determined after unblinding that the subject received a treatment other than the one to which they were randomized, safety tables will still be based on the randomized treatment for the SS. However, additional safety tables based on the actual treatment received may also be prepared whereby all data taken on or after the 1st administration of CZP is summarized according to the CZP treatment group no matter which treatment they were randomized to. The efficacy analyses will strictly follow the intention to treat principle, and no correction for receiving incorrect treatment will be performed.

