## 11 SAFETY ANALYSES

The SS will be utilized for safety analyses.

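### The main safety tables stay on randomized treatment even for subjects known to have received the other double-blind treatment, and the as-treated tables are optional

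*SAP*

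**What the plan says.** The rule is in the last paragraph of SAP Section 3.6. Its trigger is: "If it is determined after unblinding that the subject received a treatment other than the one to which they were randomized". In that case "safety tables will still be based on the randomized treatment for the SS". The alternative is permitted but not required: "additional safety tables based on the actual treatment received may also be prepared". For those optional tables the paragraph already gives a working rule, under which data from the first CZP administration onward go to the CZP group whatever the randomization. Efficacy is settled separately: "The efficacy analyses will strictly follow the intention to treat principle".

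No other section overrides this. Section 3.5.3 defines the population without an as-treated rule: "The Safety Set (SS) will consist of all subjects in the RS who have received at least one dose of study medication". Section 11 adds only that "The SS will be utilized for safety analyses". The pooled adverse event column in Section 3.6 takes its double-blind part from the randomized arm: "Total CZP incl DB and OL (includes randomized CZP 200mg Q2W and AEs starting in the open-label CZP period". The second pooled column, which adds the extension period, is built in the same way.

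**The concern.** Grouping by randomization protects the efficacy comparison, and the paragraph secures that in its own sentence. In a safety table, the same grouping puts a known CZP exposure, and any event it causes, in the placebo column. A CZP-randomized subject who received only placebo has the opposite effect on the other column and lowers the CZP rate. If CZP raises risk, both errors shrink the expected difference, which is the wrong direction for a safety comparison.

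Two features add to this. The decision to produce the as-treated tables would be taken after unblinding, so it is not fixed in advance. And because the Total CZP columns start from the randomized arm, a double-blind event on CZP given in error is absent from the pooled CZP experience as well.

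**Working it through.** The plan attaches no figure to this rule, so there is nothing of its own to reproduce. The only input taken from it is 150 subjects per arm (Section 2.4: 300 in total, 1:1). The misdosing counts and event rates below are assumptions.

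**Average effect, placebo subjects given CZP throughout.** Let k placebo-randomized subjects carry the CZP risk p1 while the rest carry p0. The placebo rate as tabulated is (p0 × (150 − k) + p1 × k) / 150.

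- p1 = 3%, p0 = 1%, k = 1: (1.49 + 0.03) / 150 = 1.013%. Risk ratio 3 / 1.013 = 2.96, against a true 3.00.
- k = 3: (1.47 + 0.09) / 150 = 1.04%. Risk ratio 2.88.
- k = 15: (1.35 + 0.45) / 150 = 1.20%. Risk ratio 2.50.
- p1 = 5%, p0 = 1%: risk ratio 4.87 for k = 1 and 4.63 for k = 3, against a true 5.00.

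**The reverse error.** One CZP-randomized subject given only placebo, at 3% and 1%: the CZP rate becomes (4.47 + 0.01) / 150 = 2.987%, and the risk ratio is 2.99.

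**When the misdosed subject has the event.** Take one placebo-randomized subject on CZP from the first dose, so that the as-treated denominators are 151 and 149.

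| Events, as treated | As treated | As randomized |
|---|---|---|
| 1 vs 0 | 1/151 (0.66%) vs 0/149 | 0/150 vs 1/150 (0.67%) |
| 4 vs 2 | 4/151 (2.65%) vs 2/149 (1.34%) | 3/150 vs 3/150 (2.00% each) |

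In the first row, the only event on CZP appears only under placebo.

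Section 11.2 also has two displays with thresholds: a table of terms with CZP incidence of at least 1% and above placebo, and a relative-risk plot of terms above 1% on CZP. A term with two events on CZP, one of them in the misdosed subject, is 2/151 (1.32%) vs 0/149 as treated and qualifies for both. As randomized it is 1/150 (0.67%) in each arm and qualifies for neither.

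**The case against.** The strongest reply is that this is a contingency with a very small expected effect, and that most of the remedy is already written. Section 3.6 foresees misdosing and drafts the as-treated rule. Nor would a misplaced event be invisible: Section 3.1 lists all data by subject, Section 11.2 adds listings of all, serious and fatal treatment-emergent events, and its antibody-status table is restricted to subjects exposed to CZP and events after their first CZP dose. This stands as far as it goes. It limits the size, but none of these outputs replaces the main tables.

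The as-treated rule also has a bias of its own. A placebo subject given one stray CZP dose would have all later placebo time counted as CZP, which dilutes the exposure-adjusted rates. This stands too, but one such subject can add at most one subject's exposure, about 1/150 = 0.67% of the CZP arm's if all subjects complete.

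A reader might infer three stronger things that the documents do not support.

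- *That the rule contradicts the open-label handling.* It does not. Open-label events are assigned by study period (Table 11–1), and those columns are themselves labelled by randomized arm (Section 3.6).
- *That every dosing error pulls the arms together.* This holds only in expectation and if CZP raises risk. A CZP subject given an occasional placebo dose stays under CZP on either basis.
- *That one misdosed subject typically shrinks a difference as much as the single-event examples suggest.* A split of 3/151 vs 0/149 (2.0 points) becoming 2/150 vs 1/150 (0.7 points) requires the misdosed subject to be one of the three with the event. With events falling at random, that has probability 3/151, about 2%. On average the placebo rate rises by 1.99% / 150 = 0.013 points, and the difference goes from 1.99 to about 1.97.

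**Conclusion.** The point holds as a fault in the rule, with a modest and conditional consequence. The main safety tables are grouped on a basis known to be wrong for the subjects concerned, and the correct grouping is left to a choice made after unblinding. If CZP raises risk, the bias is toward no difference in expectation: nil without misdosing, and a risk ratio of 2.96 or 2.88 in place of 3.00 with one or three misdosed placebo subjects under the assumed 3% and 1%. It becomes visible mainly when a misdosed subject has a rare serious event, which is then counted under placebo and missing from the Total CZP columns. It concerns double-blind dosing errors only, since CZP given in the planned open-label and extension periods has its own columns. No efficacy result is affected. All sizes rest on assumed misdosing counts and event rates, and on misdosed subjects carrying the full CZP risk.

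**What to change.** In Section 3.6, change 'may' to 'will' for the tables by actual treatment and make treatment received the basis of the main Safety Set tables, using the rule already in that paragraph (data from the first CZP administration counted under CZP). Then:

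- Align the exposure calculations in Section 11.1 and both Total CZP columns with that rule, so that numerators and denominators count the same subjects. If the error begins after the first dose, say that exposure is split at that date and that the subject counts in both columns.
- List the misdosed subjects with their dosing dates.
- Keep the as-randomized safety tables as supplementary. With the listing, they show any case where an isolated CZP dose has moved later placebo time to CZP.

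The cost is a few sentences in Sections 3.6 and 11.1, one listing, and a second set of tables only if misdosing occurred. If none occurred, no safety table changes.

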### **3.7 Center pooling strategy**

Due to the anticipated low number of subjects per center, region is used as a randomization stratification factor. The regions utilized in the IXRS system (as described in [Section 2.3.6](#)) will be used to pool centers for statistical analysis. Verification that sufficient subjects within each region exist for meaningful statistical analysis will be performed prior to unblinding.

### **3.8 Coding dictionaries**

Medical history and AEs will be coded using the latest version available for use at the time of study lock of Medical Dictionary for Regulatory Activities (MedDRA). Medications will be coded using the World Health Organization Drug Reference List (WHO-DRL).

### **3.9 Changes to protocol-defined analyses**

The protocol stated that ADAb concentrations above 2.4 unit/ml would be defined as ADAb positive. However, during the trial it was noted that the background sample noise could only be determined during the sample analyses and hence the cut point cannot be pre-specified. Therefore the immunogenicity sections of the SAP were updated.

The protocol defines a plus/minus one week window for the Week 156 time point. However at least a plus/minus 4 week window will be used in the analysis due to the Corona Virus Disease 2019 (COVID-19) pandemic, with an even more generous lower boundary to the window for patients who had their first dose post-Week 50 before the SFE informed consent date.

## **4 STATISTICAL/ANALYTICAL ISSUES**

### **4.1 Adjustments for covariates**

Statistical models may be adjusted for covariates. Any such adjustments will be described in the context of the analyses to be performed.

### **4.2 Handling of dropouts or missing data**

#### **4.2.1 Primary efficacy variable**

For analysis purposes, the primary efficacy variable is defined as a composite endpoint in which it is necessary to achieve ASDAS-MI at Week 52 and to remain on randomized double-blind study treatment through Week 52 in order to be considered a responder ([Section 8.1](#)). Subjects with missing ASDAS-MI at Week 52 are considered non-responders and therefore this composite endpoint definition does not allow for a missing response status and no formal method for handling missing data is needed in the primary efficacy analysis. However, in order to assess the impact of various missing data assumptions on the analysis, additional sensitivity analyses of the primary efficacy variable will be performed as follows:

- Including observed data at Week 52: The observed data at Week 52 will be used and analyzed according to randomized treatment, regardless of whether or not the subject is still on his/her randomized double-blind study treatment at that time. Therefore, this is no longer a composite endpoint and subjects will be a responder based solely on if they achieve ASDAS-MI response. Despite efforts to continue to collect data on all subjects (even if they discontinue the double-blind study treatment), there may still be subjects with missing data at Week 52. Such subjects will be considered as non-responders. The same logistic regression model specified for the primary analysis will be used.
- Multiple imputation: The MCMC method will be used to impute intermittent missing data. The resulting multiply imputed data sets will be monotone missing and will be imputed using monotone regression (assuming a MAR pattern). Note that the multiple imputation procedure will be done on the continuous ASDAS variable, which will be dichotomized for the logistic regression analysis. ASDAS data collected after the discontinuation of double-blind study treatment will be treated as missing in the original data set for this sensitivity analysis and hence will not be used for analysis or imputing values.
- Tipping point analysis: In this analysis, various assumptions will be made about average outcomes among the subsets of subjects who prematurely discontinued double-blind study treatment. Various “delta adjustments” will be made to the assumed responses among missing data in each treatment arm with varying degrees of plausibility (O’Kelly, 2014). The goal of the tipping point analysis is to identify assumptions about the missing data under which the conclusions change, i.e., under which there is no longer evidence of a treatment effect. Then, the plausibility of such assumptions would be discussed. Further details of this procedure are described in [Section 8.1.3.3](#).
- Observed case analysis: This analysis will only include the observed data for subjects still on the original double-blind study treatment. Data collected after the discontinuation of double-blind study treatment and all other missing data will be excluded from the analysis. The same logistic regression model specified for the primary efficacy analysis will be performed.

For Canada (and any other country where applicable or where requested by Regulatory Authorities), the primary efficacy variable is ASAS40 at Week 12 instead of ASDAS-MI at Week 52. For this reason, the above analyses will be repeated for ASAS40 at Week 12 with the composite endpoint analysis being the primary analyses.

#### 4.2.2 Secondary efficacy variables

ASAS40 at Week 12, although a secondary efficacy variable for the USA, is described within [Section 4.2.1](#) due to its status as a primary efficacy variable in other parts of the world.

The primary analysis method for the binary secondary efficacy variable(s), ASAS40 at Week 52, will be the same as that described above for the primary efficacy variable, ASDAS-MI. That is, a subject will be considered a responder only if the double-blind treatment course is completed and if ASAS40 is achieved. The sensitivity analyses of the secondary binary efficacy variable(s) (ASAS40 at Week 52 as described in [Section 8.2](#)) will be as follows:

- Including observed data at Week 52 (or Week 12 as applicable): As described for the primary efficacy variable.

- Multiple imputation: As described for the primary efficacy variable. Note that as ASAS40 is a composite of 4 different variables, the multiple imputation procedure will be performed on each of these components, and the ASAS40 response will be derived based on the multiply imputed datasets.
- Reference-based multiple imputation: This procedure will impute missing data as well as data collected at time points after the discontinuation of the double-blind study treatment for both the CZP and placebo groups. This procedure will use an imputation model developed based on data from the placebo group (Mallinckrodt, 2013). The estimand being evaluated in this case is the difference in the outcome of improvement in all randomized subjects at the planned endpoint, attributable to the initially randomized medication, which has been referred to as “estimand 6” (Mallinckrodt, 2012).
- Observed case analysis: As described for the primary efficacy variable.

For the continuous secondary efficacy variables (BASFI and BASDAI at Week 52 and 12, and SI joint SPARCC score at Week 12), the primary analysis method will be based on a referenced based multiple imputation procedure (details described in [Section 8.2](#)). The following sensitivity analyses will also be performed

- Including observed data at Week 52 (or Week 12 as applicable): As described for the primary efficacy variable
- Multiple imputation: As described for the primary efficacy variable.
- Observed case analysis: As described for the primary efficacy variable
- Last Observation Carried Forward (LOCF): If there is missing data at the double-blind time point of interest, the last available post-Baseline measurement will be carried forward to that time point (including any previous scheduled or unscheduled visits in double-blind or open-label periods). Using the date that the observation was recorded, data will be carried forward to all missing double-blind visits up until the time point of interest even if the subject has withdrawn from the study or entered the open-label period. For example, a subject withdrawing from double-blind at Visit 14 /Week 24 and entering OL-CZP will proceed to have a open-label visits at weeks 0, 2 and 4 post double-blind withdrawal followed by assessments every 12 weeks until 52 weeks post randomization. Using the date of the open-label visits, the number of weeks post randomization will be calculated to allow data to be carried forward to all subsequent missing double-blind visits. This will not apply for the analysis of SI joint SPARCC score at Week 12 since there are no measurements collected between Baseline and Week 12.

There will be no imputation or other method for handling missing data for the secondary efficacy variable, number of subjects without relevant changes to background medication. Further details on the derivation and analysis of this variable are described in [Section 8.2](#).

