### 3.2.1.3 Open-label period

The open-label period starts when subjects have discontinued the double-blind treatment period prior to start of the SFE period and take their first dose of open-label CZP or other treatment. The open-label period ends when:

- the subject takes their first dose of OL-CZP in the SFE period, for subjects continuing into the SFE
- the later of Week 52 visit and last administration of OL-CZP or other treatment, for subjects who complete the 52 week main phase of the study and do not continue into the SFE
- the subject discontinues the study prior to the week 52 visit (WD visit) and does not fall into the above categories.

Subjects switching from double-blind treatment to OL-CZP treatment and then to OL-OT will have an OL-CZP and an OL-OT period.

Subjects continuing on the study with other treatment visits, but without taking other medication will be allocated to the OL-OT period although will not be considered as starting other treatment in that period. A medical review of all cases will be performed prior to the database lock to identify subjects with valid administration of other treatment. Start and end dates of identified other treatments will be taken from the concomitant medication page.

The use of open-label period data for efficacy is described in detail in the relevant efficacy sections in [Section 8](#). If applicable, open-label period data for efficacy will be mapped to the corresponding time-point post baseline for analysis. E.g. if a subject performs an open-label

Week 12 visit at 26 weeks post-baseline, corresponding efficacy data will be considered “week 26” assessments.

Open-label visit-based safety data (such as laboratory data and vital signs data) will in general be summarized and listed as separate visits from the double-blind period visits. However, open-label visits will still be presented by the double-blind treatment groups of CZP 200mg Q2W and placebo. In general, OL-OT safety data will not be presented in tables, but only listed.

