#### **4.2.3 Other efficacy variables**

For the analysis of the double-blind 52-week treatment period, other binary efficacy variables will be treated in the same way as the primary analysis of the primary efficacy variable (composite endpoint). That is, a subject will be considered a responder only if the response is achieved and if the subject is still on their randomized double-blind study treatment at the time

when the variable is evaluated. Analyses of other continuous efficacy variables will be based on LOCF. A sensitivity analyses will be performed on all other efficacy variables using observed case analysis as described for the primary endpoint in [Section 4.2.1](#).

For analysis of the Week 156/SFE-WD visit data, binary efficacy variables will be analyzed using the non-responder imputation (NRI) approach; that is, where the denominator is all subjects in the SFE-FAS for the given treatment group. A subject will be considered a responder only if the response criterion of the given variable is achieved. All other subjects will be counted as not responding e.g. subjects who have not achieved the given outcome and all subjects with missing data are set to non-response.

An observed case analysis of binary efficacy variables at Week 156/SFE-WD will be performed. The Observed Case analysis at Week 156, will consider a subject a responder only if the response is achieved. Non-response at Week 156 visit will be counted as non-responders. Early withdrawals or subjects with missing data will be considered missing in this analysis. The sensitivity analysis of the Observed Case analysis at Week 156/SFE-WD will consider a subject as a responder if response is achieved at Week 156/SFE-WD visit such that both subjects with a Week 156 visit (subjects who complete) and subjects with early withdrawal visits and efficacy results meeting the criteria of response, will be counted as a responder. Subjects with missing data will be considered missing in this analysis.

For continuous efficacy variables, the observed data at Week 156/SFE-WD visit will be analyzed. This will summarize efficacy data for completers and subjects with early withdrawal visits during SFE together. In addition, the efficacy data collected at Week 156 for completers only will be summarized.

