### **8.2.3 Supportive and sensitivity analyses of the secondary efficacy variables**

Descriptive statistics (number of available observations [n], mean, median, standard deviation, minimum and maximum) will be provided for all secondary efficacy variables. The descriptive analyses will be covered in the tables summarizing the variables over time.

Sensitivity analyses of the secondary binary efficacy variables (ASAS40 at Weeks 12 and 52) as described in [Section 8.2](#) will be as follows:

- Including observed data at Week 52 (or Week 12 as applicable): As described for the primary efficacy variable in [Section 8.1.3.1](#).
- Multiple imputation: As described for the primary efficacy variable in [Section 8.1.3.2](#). Note that as ASAS40 is a composite of 4 different variables, the multiple imputation procedure will be performed on each of these components, and the ASAS40 response will be derived prior to Step 5 based on the multiply imputed datasets.
- Reference-based multiple imputation: As described in [Section 8.2.2.2](#).
- Observed case analysis: As described for the primary efficacy variable in [Section 8.1.3.4](#).

The sensitivity analyses of secondary continuous efficacy variables (the change from Baseline in BASDAI and BASFI at Weeks 12 and 52, the change from Baseline in the SI joint SPARCC

score at Week 12, the change from baseline for ASQoL at Week 52 and the change from baseline for Nocturnal Spinal Pain at Week 52) will be as follows:

- Including observed data at Week 52 (or Week 12 as applicable): As described for the primary efficacy variable in [Section 8.1.3.1](#)
- Multiple imputation: As described in [Section 8.2.3.1](#)
- Observed case analysis: As described for the primary efficacy variable in [Section 8.1.3.4](#).
- Last Observation Carried Forward (LOCF): If there is missing data at the time point of interest, the last available post-Baseline measurement will be carried forward to that time point (including scheduled or unscheduled visits). This will not apply for the analysis of SI joint SPARCC score at Week 12 since there are no measurements collected between Baseline and Week 12.

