### 8.3 Analysis of other efficacy variables during the double-blind 52-week treatment period

The efficacy analyses described in this section are not part of the multiplicity-controlled testing procedure described in [Section 8](#). The p-values reported for these analyses will not be adjusted for multiplicity and will be considered nominal. Derivations for these other efficacy variables can be found in [Section 8.3.1](#).

Continuous other efficacy variables will be analyzed using an ANCOVA model including Baseline score as a covariate, and fixed effects for treatment group, region, and MRI/CRP classification. The treatment differences and corresponding 95% CIs will be calculated based upon the adjusted least squares means. Missing values or values observed after discontinuing the double-blind study treatment will be imputed using LOCF. In addition, as described in [Section 4.2.3](#), an observed case analysis will also be performed for subjects still on the original double-blind study treatment. Tables for continuous variables will display descriptive statistics for Baseline, absolute values and change from Baseline at post-Baseline time points.

Categorical other efficacy variables will be analyzed using a logistic regression model with factors of treatment group, region, and MRI/CRP classification (MRI+/CRP+; MRI+/CRP-; MRI-/CRP+). If the logistic regression model is unable to converge, then the MRI/CRP classification variable may be dropped from the model to facilitate convergence. Tables for the binary variables will display the responder rates for the various time points. Analyses will be presented in 2 ways (as described in [Section 4.2.3](#)). First, they will be presented where the denominator is all subjects in the FAS for the given treatment group. This is essentially a NRI approach as subjects who have not achieved the given outcome (whether observed or not) or subjects who discontinue double-blind study treatment are considered as not having responded. Second, the responder rates will be presented for the FAS using Observed Case data. Subjects still on the original double-blind study treatment and with response will be analyzed, with the denominator based on the number of observed values at the given time point.

Continuous other efficacy variables to be analyzed using change from Baseline are:

- BASDAI and BASFI at Weeks 1, 2, 4, 8, 16, 20, 24, 28, 32, 36, 40, 44, 48
- ASDAS at Weeks 2, 4, 8, 12, 16, 20, 24, 28, 32, 36, 40, 44, 48, and 52

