- $50$  (10 mg piroxicam score)  $\times 60$  (2 months)  $\times 2/7$  (1–3 days/week)/ $180$  (6 months) = 4.8

In this example the total score for the 6 month period is 42.9 (38.1 plus 4.8).

For the observed case analysis, only intervals that end on or prior to end of the double-blind treatment period will be included. For the LOCF analysis, all data will be included for all intervals up to Week 52 (1 year) irrespective of whether the subject is on double-blind or open-label study medication.

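### LOCF carries open-label values forward in SAP Section 4.2.2 but excludes them in Section 8.3, so the same instrument follows opposite rules at Week 48 and Week 52

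*SAP*

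**What the plan says.** **Section 4.2.2, secondary continuous variables, sensitivity analysis.** The last available post-Baseline value is carried forward, "including any previous scheduled or unscheduled visits in double-blind or open-label periods", and this continues "even if the subject has withdrawn from the study or entered the open-label period". A worked example follows a subject who leaves double-blind treatment at Week 24 for open-label CZP: from the open-label visit dates, "the number of weeks post randomization will be calculated to allow data to be carried forward to all subsequent missing double-blind visits". Under Section 3.2.1.3 the open-label period begins when subjects "take their first dose of open-label CZP or other treatment", so values on open-label CZP and on other treatment both qualify.

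**Section 8.2.3, the same sensitivity analysis restated.** Here "the last available post-Baseline measurement will be carried forward to that time point (including scheduled or unscheduled visits", and the bracket closes there. Nothing is said about periods.

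**Sections 4.2.3 and 8.3, other continuous variables, main analysis.** Section 4.2.3 says only: "Analyses of other continuous efficacy variables will be based on LOCF". Section 8.3 supplies the rule: "Missing values or values observed after discontinuing the double-blind study treatment will be imputed using LOCF".

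**Section 8.3.1.11, ASAS-NSAID score.** This is one of the Section 8.3 variables, yet its LOCF analysis uses all intervals to Week 52 "irrespective of whether the subject is on double-blind or open-label study medication".

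**Sections 8.2.1.2 and 8.2.1.3.** BASDAI and BASFI data collected after double-blind treatment ends are set to missing.

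**The concern.** A value that must itself be replaced by LOCF cannot also be the value carried forward. Section 8.3 therefore allows only on-treatment values as the source, while Section 4.2.2 explicitly allows later ones. The two sections cover different variable classes, but the classes are split by visit within an instrument, so the two rules meet in a single time course. A reader who follows LOCF estimates for BASDAI from Week 48 to Week 52 would see a change of method as well as a change of time.

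Under Section 4.2.2, a placebo subject who moved to open-label CZP contributes a CZP value to the placebo mean. If more placebo than CZP subjects switch and improve, the Week 52 LOCF difference shrinks for a reason unrelated to the randomized comparison on double-blind treatment.

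**Working it through.** **Texts side by side**

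| Variable and visit | Governing text | Open-label values carried? |
|---|---|---|
| BASDAI, BASFI, Week 48 | 8.3 | No |
| BASDAI, BASFI, Weeks 12 and 52 | 4.2.2 | Yes |
| BASDAI, BASFI, Weeks 12 and 52 | 8.2.3 | Not stated |
| Nocturnal spinal pain, Week 48 | 8.3 | No |
| Nocturnal spinal pain, Week 52 | 8.2.3, read with the 4.2.2 definition | Yes, if 4.2.2 applies |
| ASAS-NSAID, to Week 52 | 8.3 general rule | No |
| ASAS-NSAID, to Week 52 | 8.3.1.11 | Yes |

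The list in Section 4.2.2 names BASDAI, BASFI and SPARCC only. Nocturnal spinal pain comes under the secondary LOCF through Section 8.2.3, so its row relies on the Section 4.2.2 definition applying to the whole class.

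The cross-references do not settle it. Section 3.2.1.3 sends the reader to Section 8 for the use of open-label efficacy data, and Section 8 sends missing-data handling back to Section 4.2. Section 3.9 is silent.

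**Size, illustration only**

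The SAP gives no switching rates and no LOCF effect sizes, so there is no plan figure to reproduce. All inputs here are assumptions, as mean BASDAI changes from Baseline: double-blind completers -3.5 (CZP) and -2.0 (placebo); last double-blind value of those who stop, -0.5; value after open-label CZP, -3.0. Let q be the proportion stopping in an arm and s the proportion of those who move to open-label CZP.

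- 8.3 rule: arm mean = (1 - q) × completer mean + q × (-0.5)
- 4.2.2 rule: arm mean = (1 - q) × completer mean + q × [s × (-3.0) + (1 - s) × (-0.5)]

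With 60% of placebo and 30% of CZP subjects stopping, and s = 1:

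- 8.3: placebo 0.4 × (-2.0) + 0.6 × (-0.5) = -1.10; CZP 0.7 × (-3.5) + 0.3 × (-0.5) = -2.60; difference -1.50.
- 4.2.2: placebo 0.4 × (-2.0) + 0.6 × (-3.0) = -2.60; CZP 0.7 × (-3.5) + 0.3 × (-3.0) = -3.35; difference -0.75.

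| Stopping, placebo / CZP | s | 8.3 | 4.2.2 | Loss |
|---|---|---|---|---|
| 20% / 20% | 1.0 | -1.20 | -1.20 | 0% |
| 20% / 10% | 0.7 | -1.50 | -1.33 | 11% (0.17/1.50) |
| 40% / 20% | 1.0 | -1.50 | -1.00 | 33% (0.50/1.50) |
| 60% / 30% | 1.0 | -1.50 | -0.75 | 50% (0.75/1.50) |

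When s and the post-switch value are the same in both arms, the gap between the rules is (CZP stopping - placebo stopping) × s × (-3.0 + 0.5). It vanishes when stopping is equal.

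A second set of assumptions (completers -3.0 and -1.5, last double-blind value 0, all switching, open-label value -1.5 or -3.0) shows the same pattern. With 20% stopping in both arms, both rules give -1.2. With 40% against 10%, 8.3 gives -1.8 and 4.2.2 gives -0.9 to -1.35. With 60% against 10%, 8.3 gives -2.1 and 4.2.2 gives -0.6 to -1.35. One half is therefore the end of the first set of scenarios, not a ceiling.

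**The case against.** The strongest reply is that these are not two definitions of one analysis. Section 4.2.2 governs a sensitivity analysis of the secondary variables and Section 8.3 governs the other variables. That is correct, and it limits the point. A reader might infer that the LOCF tables for ASDAS, the ASAS components or SF-36 could be programmed either way. They could not: Section 8.3 states the rule for that class. What remains is the split within an instrument by visit, and the incomplete restatement in Section 8.2.3.

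A reader might also infer that LOCF under Section 4.2.2 merely repeats the analysis that includes observed data, or says nothing about missing data. It overlaps for switchers with a Week 52 value, but it still imputes subjects who have none, so it is not redundant.

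Nor do Sections 8.2.1.2 and 8.2.1.3 alone decide the matter. They cannot bar every use of post-discontinuation data, because the analysis including observed data needs it. They show which way the derivations lean.

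The open-label clause and its example were added on purpose in SAP Amendment 2, and carrying values regardless of treatment is a coherent sensitivity analysis. The documents therefore do not make that choice an error in itself; the fault is the inconsistency. Likewise, ASAS-NSAID is built from medication dates and may deserve its own rule, but Section 8.3.1.11 does not say that it departs from Section 8.3.

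**Conclusion.** The point holds as an inconsistency in the current text that should be corrected. BASDAI, BASFI and, if the Section 4.2.2 definition covers it, nocturnal spinal pain follow opposite LOCF rules at Week 48 and Week 52. ASAS-NSAID contradicts the general rule of its own class.

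No confirmatory result depends on it. The primary endpoint is a composite responder definition, the continuous tests in the fixed sequence use reference-based multiple imputation, and the Section 8.3 p-values are nominal.

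A reader might take the illustration as evidence of a definite loss of effect. The documents do not support that. The size depends on unequal stopping between arms and on how far switchers improve, and the SAP quantifies neither. Unequal stopping is plausible: Section 8.1.3.2 lets investigators stop treatment for non-responders, and Section 2.4 expects 40% response on CZP against 20% on placebo. Within the first set of assumed inputs the difference runs from none to half of the effect. Section 4.2.2 also covers Week 12, when there has been less time to switch.

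**What to change.** Use one LOCF rule for the same instrument at all visits.

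- **Preferred, to match Sections 8.3, 8.2.1.2 and 8.2.1.3:** carry forward the last post-Baseline value recorded up to discontinuation of double-blind treatment, and set later values to missing first. Remove the open-label clause and the Week 24 example from Section 4.2.2, state the same rule in Section 8.2.3, and point to it from Section 4.2.3. Keep open-label values for the analysis that includes observed data.
- **ASAS-NSAID:** mark Section 8.3.1.11 as an explicit exception, or align it.
- **If the sponsor prefers LOCF including open-label data:** label it as a separate supplementary analysis, apply it at all visits, and align Sections 8.2.1.2, 8.2.1.3, 8.2.3 and 8.3.

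The cost is SAP wording, one derivation flag and a re-run of the LOCF tables.
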